4.2.6.2 Clinical laboratory safety assessment

Clinical laboratory data include hematology, chemistry, CRP, CSF, blood gas and base excess, urinalysis, and urine output. Descriptive statistics (including n, mean, SD, minimum, median, and maximum) of observed results and change from baseline will be presented for continuous clinical laboratory results by age cohort and overall for the Safety Analysis Set.

In addition, the following summaries at each applicable visit will also be provided by age cohort and overall:

- Shift tables showing the number of patients with changes from low, normal, or high values from baseline
- Shift tables showing the number of patients with urinalysis changes from baseline to each category (negative, trace, positive)
- The number and percentage of patients with abnormal values using the PCS criteria in [Appendix B](#)

Listings of values for each patient will be presented by age cohort with abnormal or out-of-range values flagged. All laboratory results for each patient will be listed for the Safety Analysis Set.

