- Direct Coombs' Test Seroconversion: seroconversion from a negative to a positive test result occurred in more patients receiving ceftaroline fosamil than comparator drugs in pooled data from 4 Phase III clinical trials. If anaemia develops during or after treatment with ceftaroline fosamil, drug-induced haemolytic anaemia should be considered.
- Development of Drug-Resistant Bacteria: prescribing ceftaroline fosamil in the absence of a proven or strongly suspected bacterial infection is unlikely to provide benefit to the patient and increases the risk of the development of drug-resistant bacteria.
- Adverse Reactions: in the four pooled Phase III clinical trials, SAEs occurred in 98/1300 (7.5%) of patients receiving ceftaroline fosamil and 100/1297 (7.7%) of patients receiving comparator drugs. Treatment discontinuation due to adverse events occurred in 35/1300 (2.7%) of patients receiving ceftaroline fosamil and 48/1297 (3.7%) of patients receiving comparator drugs with the most common adverse events leading to discontinuation being hypersensitivity for both treatment groups at a rate of 0.3% in the ceftaroline fosamil group and 0.5% in the comparator group.
- No adverse reactions occurred in greater than 5% of patients receiving ceftaroline fosamil. The most common adverse reactions occurring in >2% of patients receiving ceftaroline fosamil in the pooled Phase 3 clinical trials were diarrhea, nausea, and rash.

No clinical drug-drug interaction studies have been conducted with ceftaroline fosamil. There is minimal potential for drug-drug interactions between ceftaroline fosamil and CYP450 substrates, inhibitors, or inducers; drugs known to undergo active renal secretion; and drugs that may alter renal blood flow.

Safety and effectiveness in pediatric patients <2 months of age have not been established.

Dosage adjustment is required in patients with moderate or severe renal impairment and in patients with end-stage renal disease ($\text{CrCl} < 15 \text{ mL/min}$).

The PK of ceftaroline in patients with hepatic impairment has not been established.

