 h. At baseline, obtain results of CXR, CT scan, or other imaging tests (eg, echocardiogram, CT, MRI, sonography) if performed as part of the patient's regular medical care within 72 hours before first dose of study therapy.
 i. Refer to the inclusion criteria ([Section 3.1](#)) for list of tests. Recommended to repeat at least every 7 days. If immature neutrophils are available, calculate I/T neutrophil ratio using the formula: I/T ratio=Immature cells/Total (mature+immature).
 j. If clinically indicated.
 k. For patients who have been hospitalized for ≥ 8 hours, calculate urine output over the last 8-hour period.
 l. Patients will be randomly assigned (1:1) to one of the following PK sample collection schedules collected after any dose between the end of the 4th infusion of ceftaroline fosamyl and before EOT or Study Day 14 (whichever is earlier):
 PK Schedule 1: at the end of the ceftaroline fosamyl infusion (± 5 minutes) and 3 to 4 hours after the end of the infusion
 PK Schedule 2: 15 minutes to 2 hours after the end of the ceftaroline fosamyl infusion and 5 to 7 hours after the end of the infusion (before the start of the next infusion).
 m. PK blood samples are NOT to be drawn if the patient received a blood or blood component transfusion within the past 24 hours. For patients who are at risk from additional blood loss, collection of PK samples will require assessment by the investigator.
 n. Matching blood sample to be collected only if 2 PK blood samples have not been collected already. The matching blood sample replaces one of the PK samples, so that the total number of PK samples does not exceed 2.

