7.7. Concomitant and other treatments

All prior medications (taken or received within 7 days before the first dose of study therapy) and all concomitant medications (taken during the study), including, but not limited to, all antimicrobials, parenteral nutrition, and blood and blood-component transfusions will be documented. For patients who are being breast fed, all medications taken by the lactating mother for 3 days before first dose of study therapy through SFU will also be recorded.

Concomitant antibacterial therapy is not permitted except in the case of clinical failure.

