3. PRIMARY AND SECONDARY VARIABLES

For the calculation or derivations of the variables in this section, baseline will be defined as the last non-missing value before the start of study therapy. Change from baseline variables will be calculated for clinical laboratory tests and vital signs parameters as the post-treatment value minus the value at baseline. The visit windows for EOT, TOC, and SFU are defined in [Table 2](#) for efficacy analyses.

Study days are to be calculated starting from the onset of the first dose of study therapy, in 24-hour increments. If a date is prior to the first study therapy dose date (eg, date of LOS diagnosis, prior medication start date) then the study day will be calculated as (past date – first

study therapy dose date); if the assessment date is on or after the first study therapy dose date then the study day will be calculated as (assessment date – first study therapy dose date + 1). Durations in days will be calculated as (end date – start date +1).

Table 2 Visit Windows for EOT, TOC, and SFU

Visit	Protocol-defined Window
End of IV therapy (EOT)	Within 24 hours of completion of the last infusion of study drug
Test of cure (TOC)	8 to 15 days after the last dose of study drug
Safety follow-up (SFU)	28 to 35 days after the last dose of study drug

NB. Since there is no per protocol population defined for this study, scheduled visits will be used for MITT analyses and derived analysis windows will not be evaluated.

For analyses purposes, nominal visit data was used.

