4. ANALYSIS METHODS

4.1 General principles

All analyses will use SAS® version 9.1.3 or higher. Summary tables will be organized by age cohort and overall. All available data for each analysis set will be used in the analyses, and a subset of key safety, efficacy, and PK data will be included in listings. No statistical hypothesis testing will be performed. Confidence intervals (CI) will be two-sided 95% CIs.

Unless otherwise noted, categorical data will be presented using counts and percentages with the denominator for percentages being the number of patients in the analysis set by age cohort. Percentages will be rounded to one decimal place; except 0% and 100% will be displayed without any decimal places and percentages will not be displayed for zero counts. Continuous variables will be summarized using the number of observations (n), mean, SD, median, minimum, and maximum. The minimum and maximum values will be displayed to the same level of precision as the raw data, the mean and median to a further decimal place and the SD to two additional decimal places.

Imputation of missing data will be performed as described within this document (see [Section 3.2.1](#) for imputation of efficacy data at EOT and TOC and [Section 3.3.2](#) for imputation of partial dates for prior and concomitant medication). Visit windowing will be performed as described in [Section 3](#).

Baseline summaries will utilize the ITT and MITT Analysis Sets. Study therapy exposure, concomitant medication, and safety analyses will utilize the Safety Analysis Set. Efficacy analyses of clinical outcome and microbiological response will utilize the MITT and Micro-ITT Analysis Sets. PK analyses will utilize the PK Analysis Set. All data will be listed.

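### The SAP has no rule for haemoglobin, haematocrit and red-cell values taken after a transfusion and no worst-value summary, so its end-of-therapy laboratory rows can understate anaemia

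*SAP*

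**What the plan says.** **The laboratory tables.** SAP section 4.2.6.2 states that "change from baseline will be presented for continuous clinical laboratory results by age cohort and overall for the Safety Analysis Set". It adds that "the following summaries at each applicable visit will also be provided by age cohort and overall", and these include "Shift tables showing the number of patients with changes from low, normal, or high values from baseline" and counts against the PCS criteria of Appendix B. For haemoglobin and haematocrit, Appendix B lists a value below 0.6 times the lower limit of normal (LLN) and a fall of more than 25% from baseline. For red cells the figures are 0.8 times LLN and 20%.

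**Which values enter.** SAP section 4.1: "All available data for each analysis set will be used in the analyses". SAP section 3, below the visit-window table: "For analyses purposes, nominal visit data was used". SAP section 3 also takes the last non-missing value before study therapy as baseline. None of these places mentions transfusion, and no lowest post-baseline value is defined.

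**When blood counts are taken.** Protocol section 5.3.1 and Table 1 require them at baseline and EOT. At other visits they are taken if clinically indicated.

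**The risk and the transfusion record.** Protocol section 1.3, under Coombs' test seroconversion: "If anaemia develops during or after treatment with ceftaroline fosamil, drug-induced haemolytic anaemia should be considered". Protocol section 7.7 provides that "blood and blood-component transfusions will be documented". The documents' only rules on transfusion and samples concern pharmacokinetics. Protocol Table 1, footnote m, says: "PK blood samples are NOT to be drawn if the patient received a blood or blood component transfusion within the past 24 hours". Protocol section 8.3.4 carries the same limit into the definition of its PK analysis set.

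**The concern.** A transfusion raises the very quantities these tables summarise, and infants with the largest falls are plausibly the likeliest to receive one. If the transfusion comes before EOT, the infant contributes a corrected value to the EOT change, shift and PCS rows. These are the only post-baseline rows planned to contain every infant. The distortion runs one way, towards no effect on haemoglobin.

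A related problem arises at the start. Baseline procedures may precede the first dose by up to 36 hours. A transfusion in that gap leaves the recorded baseline too low, so a later fall looks smaller than it was.

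At stake is how an objective laboratory signal reads in a single-arm study of 24 infants whose primary objective is safety. Two other possible signals are absent. Haemolytic anaemia is not among the adverse events of special interest (SAP section 3.1.1.1 and Appendix C), and no Coombs test is in the laboratory panel (protocol Table 2, SAP Table 3).

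**Working it through.** The plan states no figure to reproduce. The check has two parts: what the text allows, and an illustration of what follows.

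**1. Text.** Transfusions are recorded (protocol 7.7; SAP 3.3.2 treats them as medications). SAP 4.2.6.2, 4.1 and 3 contain nothing that excludes, flags or separates a later haematology value. Post-transfusion values therefore enter the tables. A low value drawn at a nominal on-treatment visit enters that visit's row. One drawn outside a nominal visit may enter no row, because no worst-value summary exists to catch it.

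**2. Illustration at EOT.** All inputs here are assumptions, not figures from the documents: baseline haemoglobin 10, 12 or 14 g/dL; LLN 10 g/dL; fall 26%, 30% or 40%; transfusion rise 2, 3 or 4 g/dL.

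- Lowest value = baseline × (1 − fall).
- EOT value = lowest value + rise.
- Change = (EOT value − baseline) / baseline.

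One case: baseline 12, fall 30%. The lowest value is 12 × 0.70 = 8.4, a fall beyond 25% and below LLN.

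| Rise (g/dL) | EOT value | Change | Fall >25%? | Shift |
|---|---|---|---|---|
| 2 | 10.4 | −13.3% | no | normal to normal |
| 3 | 11.4 | −5.0% | no | normal to normal |
| 4 | 12.4 | +3.3% | no | normal to normal |

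Whole grid (3 × 3 × 3 = 27 combinations):

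- Every lowest value is a fall of more than 25%. Only 1 of 27 EOT values still is (baseline 14, fall 40%, rise 2: −25.7%).
- The lowest value is below LLN in 24 of 27 (all except baseline 14 with a 26% fall, 10.36 g/dL). At EOT, 5 are still low, so 24 − 5 = 19 read as normal.
- The rise needed to return to a 25% fall is baseline × 0.75 − lowest value, which runs from 0.1 to 2.1 g/dL.

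These counts describe a constructed grid, not probabilities.

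**3. PCS caveat.** Appendix B does not say whether its limit column and its percent-change column combine as 'and' or 'or'. The percent column alone is used above. With LLN 10 the other limit is 0.6 × 10 = 6.0 g/dL. The lowest value in the grid is 10 × 0.60 = 6.0, which is not below it. Under an 'and' reading no infant in this grid would be PCS even before transfusion. The effect on mean change and on shifts would remain.

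**4. Weight of one infant.** In a count: 1/8 = 12.5% of a cohort and 1/24 = 4.2% overall. In the EOT mean change, compared with using the lowest value, the difference is rise / n. For rises of 2 to 4 g/dL this is 0.25 to 0.5 g/dL in a cohort of 8, and 0.08 to 0.17 g/dL in 24.

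**5. Baseline gap.** Assume a baseline sample of 10, a transfusion to 12 before the first dose, then a 30% fall to 8.4. The table shows (8.4 − 10)/10 = −16%, not −30%.

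**The case against.** A reader might infer that drug-induced haemolytic anaemia would be hidden from the safety analysis. The documents do not support that.

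- The primary outcome measures are adverse events, serious adverse events, deaths and discontinuations, not mean haemoglobin. Under protocol section 6.2.2, an abnormal result that needs intervention or further work-up should be recorded as an adverse event. A fall that leads to transfusion fits, and would appear in the tables of SAP section 4.2.6.1.
- Protocol section 5.3.1 calls for a haemolysis evaluation after a significant fall in haemoglobin or haematocrit.
- An infant whose haemoglobin is falling is the one with a clinical indication for a blood count. The shift and PCS tables are made at each applicable visit, and every laboratory value is listed. The documents give no figure for how many infants are tested at optional visits, so nothing can rest on that being few.
- Transfusions are tabulated and listed with concomitant medications (SAP sections 3.3.2 and 4.2.4).

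All of this stands, and it limits the point to the laboratory tables. It does not correct the EOT rows. Nor does the medication table reliably count transfused infants, because SAP section 4.2.4 includes maternal medications in the same summaries; the patient listing would have to be read instead.

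The PK sampling rule is also only a weak analogy. It shows that transfusion was considered for one kind of sample, but the documents give no reason for it that bears on haematology.

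A last objection concerns the remedy. Simply substituting the last pre-transfusion value gives a false zero change whenever that value is the baseline sample. This is correct, and the fix below avoids it.

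**Conclusion.** The point holds for the laboratory tables. With no transfusion rule and no worst-post-baseline summary, the EOT change, shift and PCS rows for haemoglobin, haematocrit and red cells can understate anaemia, a signal tied to a risk named in protocol section 1.3. It does not extend to the whole safety analysis: the event should still be found among the adverse events, in on-treatment rows where the low value was drawn at a nominal visit, and in the listings.

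The size cannot be computed, because the documents give no transfusion rate. The grid shows only that masking at EOT needs no extreme assumptions, and its PCS part depends on how the Appendix B columns combine. This is a cheap improvement to a descriptive analysis rather than a flaw that undermines the primary objective.

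**What to change.** In SAP section 4.2.6.2, for haemoglobin, haematocrit and red cells:

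1. Flag values taken after a red-cell transfusion to the infant. Also flag any baseline followed by a transfusion before the first dose.
2. Beside the planned tables, add change, shift and PCS summaries that use each infant's lowest post-baseline value, scheduled or unscheduled, drawn before any transfusion given after the first dose. Leave infants with a flagged baseline out of the change and shift summaries. Where no post-baseline value precedes the transfusion, show the infant as 'transfused, no pre-transfusion value' and do not carry baseline forward as zero change.
3. Add a row, by cohort and overall, counting infants whose own record (not the mother's) shows a red-cell transfusion after the first ceftaroline dose, with their lowest pre-transfusion haemoglobin.

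The cost is a little more programming on laboratory values and transfusion records already collected, provided the record identifies the blood component. No clinical procedure changes. The summaries recover a fall only where a low value was drawn; the row in item 3 covers the other transfused infants. Some transfusions will be unrelated to haemolysis, so these tables should supplement the planned ones and not replace them.

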4.2.6.3 Weight, vital signs, and oxygen saturation results

Weight, vital signs (heart rate, blood pressure, respiratory rate, temperature) and oxygen saturation (measured by oximeter) will be summarized. Descriptive statistics (including n, mean, SD, minimum, median, and maximum) of observed results and change from baseline will be presented for continuous results by age cohort and overall for the Safety Analysis Set.

Listings of values for each patient will be presented by age cohort for the Safety Analysis Set.

4.2.6.4 Other safety results

Data for physical examination by body system, imaging study results, and adjunctive therapeutic procedures related to infections will be included in ADaM datasets and presented in listings for the Safety Analysis Set.

4.2.7 Efficacy analysis

4.2.7.1 Clinical response

The number and percentage of patients with a clinical cure, clinical failure, and indeterminate clinical response at EOT and TOC will be tabulated overall and by baseline pathogen, overall and within each age cohort for the ITT, MITT and Micro-ITT Analysis Sets. A two-sided 95% CI for the observed clinical cure rate overall, within each cohort and overall will be constructed using the Jeffreys method. Sensitivity analyses will be conducted on the overall response excluding indeterminate responses.

Clinical outcome and derived response data will be listed by age cohort and patient for the ITT Analysis Set.

4.2.7.2 Microbiological response

The number and percentage of patients with a favourable, unfavourable and indeterminate microbiological response at EOT and TOC will be tabulated overall, and by baseline pathogen (overall and within each age cohort) for the MITT and Micro-ITT Analysis Sets. A two-sided 95% CI for the observed microbiological favourable rate overall within each cohort and overall will be constructed using the Jeffreys method.

The number and percentage of pathogens with a favorable microbiological response (eradication, presumed eradication) at TOC will be tabulated by baseline pathogen and baseline ceftaroline MIC (overall and within each age cohort) for the MITT and Micro-ITT Analysis Sets.

All other microbiological data including microbiological responses by pathogen and by patient, susceptibility testing and gram staining will be listed by age cohort and patient for the ITT Analysis Set.

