4.1.1.3. Microbiological assessments

Microbiological assessments should be performed preferably before any antibiotics are administered.

- If clinically indicated and performed as part of patient's regular medical care, obtain blood and urine samples for testing per [Section 5.2.1](#) and [5.2.2](#), respectively; cultures should be repeated per standard of care upon knowledge of a positive result until sterilization is confirmed
- If clinically indicated and performed as part of patient's regular medical care, obtain CSF or other specimens/tissue samples per [Section 5.2.3](#) and [5.2.4](#), respectively; cultures may be repeated per standard of care upon knowledge of a positive result.
- Obtain any prior microbiological and clinical data (eg, notes in medical records confirming worsening of signs and symptoms of sepsis) that may help determine eligibility ([Section 5.2](#))

Enrol the patient and assign to PK schedule after verifying that the patient meets all inclusion and no exclusion criteria. There should be no medically inappropriate delay in administration of study therapy.

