2.1.3 Modified Intent-to-Treat Analysis Set

The Modified Intent-to-treat (MITT) Analysis Set will include all patients who received any amount of ceftaroline fosamil and who met minimal disease criteria of LOS as described in the protocol inclusion criteria (diagnosis of sepsis within 36 hours before enrolment, defined as the presence of at least 2 clinical criteria and at least 1 laboratory criteria in the presence of or as a result of suspected or proven bacterial infection that requires IV antibiotic therapy). Patients with confirmed infection at baseline with a pathogen known to be resistant by CLSI methodologies and interpretive criteria (M100-S-28) to the study therapy received will be excluded. Patients with a confirmed fungal, parasitic, or viral pathogen as the sole cause of infection will also be excluded ([Appendix A](#)).

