Similarly, per-patient microbiological response will be categorized as favorable, unfavorable, or indeterminate as follows. Per-patient microbiological response at EOT and TOC will be derived programmatically based on individual outcomes for each baseline pathogen. In order for a patient to have a favorable per-patient microbiological response, the outcome for each baseline pathogen must be favorable (eradicated or presumed eradicated) at that time point. This includes results of blood cultures, urine cultures, CSF cultures or other specimen cultures at the time point. If the outcome for any baseline pathogen from any culture is unfavorable (persistence or presumed persistence) at that time point, the patient will be considered to have an unfavorable per-patient microbiological response. If there is an indeterminate per-pathogen microbiological response at the time point (ie, no culture result available and patient's clinical outcome was indeterminate), the patient will be considered to have an indeterminate per-patient microbiological response. For per-patient microbiological response at TOC visit, the above definition is only applicable to patients who are not clinical failures at EOT.

Patients who are clinical failures at EOT will have the corresponding per-patient microbiological outcome determined from EOT cultures and carried forward to TOC. If no EOT culture is available for patients who are clinical failures at EOT, then the microbiological outcome at TOC will be presumed persistence. Otherwise, the microbiological outcome at TOC will be determined from cultures obtained within the TOC visit window. If no culture is available in the TOC window, then the microbiological outcome at TOC will be presumed from the clinical response at TOC (if clinical cure, the microbiological outcome will be presumed eradication; if clinical failure, the microbiological outcome will be presumed persistence; if clinically indeterminate, the microbiological outcome will be indeterminate).

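### The MITT microbiological favourable rate (SAP 4.2.7.2) is by default taken over all MITT patients, including infants with no baseline pathogen, who cannot have a response

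*SAP*

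**What the plan says.** SAP 4.2.7.2 tabulates favourable, unfavourable and indeterminate microbiological response per patient at EOT and TOC: "overall and within each age cohort) for the MITT and Micro-ITT Analysis Sets. A two-sided 95% CI for the observed microbiological favourable rate". The interval is Jeffreys, within each cohort and overall. The interval sentence names no analysis set itself; it follows directly on the one that names MITT and Micro-ITT.

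Four other provisions bear on it.

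- **Who is in MITT.** SAP 2.1.3 asks for treatment with ceftaroline fosamil and the sepsis criteria "in the presence of or as a result of suspected or proven bacterial infection that requires IV antibiotic therapy". Suspected infection is enough. The set excludes "Patients with confirmed infection at baseline with a pathogen known to be resistant by CLSI methodologies and interpretive criteria" and infants whose sole confirmed cause is fungal, parasitic or viral.
- **Whether a pathogen is looked for.** Protocol 4.1.1.3, at baseline: "If clinically indicated and performed as part of patient's regular medical care, obtain blood and urine samples for testing". A culture is not guaranteed for every infant, and a culture that is taken may be negative.
- **What a response is.** For a favourable per-patient response under SAP 3.2.1.2, "the outcome for each baseline pathogen must be favorable (eradicated or presumed eradicated) at that time point". Unfavourable and indeterminate are likewise built from outcomes of baseline pathogens. There is no category for an infant who has none.
- **The denominator.** SAP 4.1 sets a default for every categorical table, "with the denominator for percentages being the number of patients in the analysis set by age cohort", which holds wherever the SAP gives no other rule. Neither 4.2.7.2 nor 3.2.1.2 notes an exception. The one explicit denominator rule, in SAP 3.2.1.1, concerns clinical response.

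**The concern.** Together these provisions count infants in the denominator who cannot enter the numerator. The MITT favourable rate then mixes two quantities: how often a pathogen was found at baseline, and how often it was cleared. A low figure could mean poor eradication or simply few positive cultures, and the Jeffreys interval would be centred on that mixture. The three categories would also fail to add to 100%, with no stated reason.

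This is more than missing detail. The SAP states a default, and following it gives a rate that does not answer the question the table poses. At stake is the reading of a descriptive secondary result, not a test or a trial decision.

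The problem lies in the overall and by-cohort per-patient rows. Rows for a single baseline pathogen concern only infants who have that pathogen.

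**Working it through.** **Inputs.** The planned size is 24, as 3 cohorts of 8 (SAP 1.3); I take all 24 as MITT. The interval is Jeffreys, two-sided 95% (SAP 4.1 and 4.2.7.2). The documents state no microbiological rate and no expected pathogen yield, so there is no figure of theirs to reproduce. The number of infants with a baseline pathogen, k, is assumed and varied from 4 to 20. All but one of the k infants are assumed favourable, so x = k − 1.

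**Formulas.** The SAP 4.1 default rate is x/24 and the pathogen-based rate is x/k. The Jeffreys limits for x out of n are the 2.5% and 97.5% quantiles of Beta(x + 0.5, n − x + 0.5), with the upper limit set to 100% when x = n.

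| k of 24 | SAP 4.1 default | Pathogen-based |
|---|---|---|
| 4 | 3/24 = 12.5% (3.6 to 29.7) | 3/4 = 75.0% (28.4 to 97.2) |
| 6 | 5/24 = 20.8% (8.4 to 39.8) | 5/6 = 83.3% (44.2 to 98.1) |
| 8 | 7/24 = 29.2% (14.1 to 48.9) | 7/8 = 87.5% (54.6 to 98.6) |
| 12 | 11/24 = 45.8% (27.3 to 65.3) | 11/12 = 91.7% (67.2 to 99.1) |
| 20 | 19/24 = 79.2% (60.2 to 91.6) | 19/20 = 95.0% (78.9 to 99.5) |

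**Ceiling.** Since x cannot exceed k, the default rate cannot exceed k/24. With k = 8 and every pathogen eradicated, the table would show 8/24 = 33.3% (17.2 to 53.2) against 8/8 = 100% (73.8 to 100).

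**Category total.** With k = 6, the favourable, unfavourable and indeterminate rows add to 6/24 = 25%.

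**One cohort.** With 8 infants, 2 with a pathogen and both favourable: 2/8 = 25.0% (5.6 to 59.2) against 2/2 = 100% (33.3 to 100).

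**Interval width.** At k = 6 the pathogen-based interval is wider: 98.1 − 44.2 = 53.9 points against 39.8 − 8.4 = 31.4. At k = 12 it is narrower: 99.1 − 67.2 = 31.9 against 65.3 − 27.3 = 38.0.

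**The case against.** The strongest reply is that the SAP already supplies the right figure. Micro-ITT (SAP 2.1.4) requires a baseline pathogen, was added deliberately in SAP V2.5, and gets the same table and interval. SAP 4.2.3 also tabulates baseline pathogens by specimen type in MITT, so yield is not hidden, although no single row for any pathogen is promised. A reader who adds the three MITT category counts recovers the pathogen-based proportion and, because a Jeffreys interval depends only on x and n, its interval too. The table shells are not among the documents, and the amendment history says programming notes were added to them, so a denominator note may exist there.

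Most of this stands, and it limits the harm. It does not remove the point. Micro-ITT is drawn from ITT, meaning all enrolled patients with signed consent, and its definition mentions neither treatment nor the MITT exclusions. It need not be the same infants as MITT patients with a pathogen.

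Two stronger readings are tempting, and the documents do not support them.

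- *That Micro-ITT certainly differs from MITT patients with a pathogen.* A difference is only possible. Appendix A lists many resistant organisms in its Never column, so infants with these may not count as having a potentially causative pathogen at all.
- *That the TOC fallback would turn infants without a pathogen into favourable responders.* The sentence is "If no culture is available in the TOC window, then the microbiological outcome at TOC will be presumed from the clinical response at TOC", and it is not limited in words to patients with a pathogen. But it assigns presumed eradication or presumed persistence, which SAP Table 7 defines for pathogens identified at baseline. With no such pathogen there is nothing to presume eradicated.

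**Conclusion.** The point holds as a minor correction. Under the stated SAP 4.1 default, the overall and by-cohort MITT microbiological rates and their intervals are diluted by infants who have no defined response, and each rate is capped at the share of infants with a baseline pathogen.

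The size depends on that share, which the documents do not give. On the assumptions above the gap runs from 12.5% against 75.0% (4 of 24 with a pathogen) to 79.2% against 95.0% (20 of 24), closing as yield rises. It would vanish if every MITT infant had a baseline pathogen, or if the unseen shells already set the denominator.

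A reader might infer that the trial will have no usable microbiological rate. That goes too far, because the Micro-ITT table provides one with its own interval. The trial is not powered for inference and plans no hypothesis test, so no error rate or sample size is affected.

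**What to change.** In SAP 4.2.7.2:

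1. State that, for MITT, the denominator of the overall and by-cohort microbiological percentages and intervals is the MITT patients with at least one baseline pathogen. For rows by pathogen, it is the MITT patients with that pathogen.
2. Show in the table, overall and by cohort, how many MITT patients have no baseline pathogen.
3. Keep the Micro-ITT table and interval alongside.

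The cost is SAP wording and table shells, with no new data and no change to the outcome categories. If the shells already carry such a note, it need only be copied into the text. The downside is smaller denominators, with very few infants in some cohorts, and wider intervals when yield is low, though not when it is higher.
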